3. STATISTICAL CONSIDERATIONS

3.1 DETERMINATION OF SAMPLE SIZE

The study is intended to test for non-inferiority in the percentage change in target ulcer area between PICO and tNPWT over a 12-week treatment period. During a review of five previous studies with venous leg ulcer and diabetic foot ulcer, with treatment of PICO or tNPWT, the mean percentage change in ulcer area was found to be approximately between 47-62%, in cases where it was considered an appropriate measure, the standard deviation ranged approximately between 21-24.5%. Using a non-inferiority margin of 12.5%, a sample size of 128 subjects will provide 80% statistical power at the (cumulative) 0.025 one-sided significance level assuming a weighted average mean healing of 60% with a worst case standard deviation of 24.5%. This was calculated using EAST 6. To allow for a 20% drop out rate throughout the 12-week treatment period, a total of approximately 160 subjects (80 per treatment) will be randomized.

The sample size randomized will include a minimum of 100 VLU to allow for a minimum of 70% power for VLU-only analysis using the above assumptions.

An interim analysis (built into the sample size) of key variables will take place after approximately 50% of target recruitment (80 subjects completed) with the stipulation that the interim will contain at least 40 VLU and 20 DFU. A recommendation may be made at this point to stop the trial prematurely due to efficacy or futility.

3.2 RANDOMIZATION

All eligible subjects will be randomized between PICO and ActiV.A.C.[®] therapy settings by means of an online randomisation system (Sealed Envelope).

Treatment will be randomized, stratified by wound type and wound size at the conclusion of the screening period (and prior to commencement of the treatment period) to prevent imbalance on these variables between the two treatment groups.

The resulting strata will be as follows:

- *Small DFU ($\leq 2 \text{ cm}^2$)*
- *Large DFU ($> 2 \text{ cm}^2$)*
- *Small VLU ($\leq 12 \text{ cm}^2$)*

- Large VLU (>12 cm²)

A blocked randomization will be used for each stratum utilizing a block size of 2 and 4. Due to visible differences between treatments, allocation to treatment will not be blinded.

3.3 INTERIM REVIEW

An interim analysis of key variables will take place after approximately 50% of target recruitment (80 subjects completed) with the stipulation that the interim will contain at least 40 VLU and 20 DFU. The interim analysis will contain a check for efficacy with an alpha spend of 0.002. A non-binding look for futility will also be performed at the same time point. The Lan and DeMets (1983) "Pocock" spending function will be used. If the efficacy boundary of 2.963, using the Z scale is exceeded ($Z > 2.963$) a recommendation will be made to terminate the trial on the basis of efficacy. Alternatively, if the futility bound of 0.559 using the Z scale is crossed ($Z < 0.559$) it will be recommended to terminate the trial prematurely due to lack of efficacy (futility). If assumptions relating to normality not hold, the corresponding p-value boundary scale values will be used.

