8. STUDY DESIGN

8.1 STUDY DESIGN

This is a multi-center, Phase 4, randomized, open-labelled, comparative-effectiveness study in subjects with at least one lower extremity wound (VLU or DFU). Approximately 160 subjects, including a minimum of 100 subjects presenting with VLU and 46 presenting with DFU, will be randomized to one of two treatment groups in an equal allocation to receive either PICO single-use NPWT system or tNPWT system, for 12 weeks, or until target ulcer closure (by surgical intervention or secondary intention), whichever occurs first.

Subject randomization to trial treatment will be conducted using an online randomization system and will be stratified by the subject's ulcer type and ulcer size (cm²) at baseline. Each stratification factor will contain two levels: Venous Leg Ulcer or Diabetic Foot Ulcer, and Small or Large Ulcer with the definition of small and large dependent on ulcer type. The result will be four possible strata:

- Venous Leg Ulcer $\leq 12\text{cm}^2$ (small)
- Venous Leg Ulcer $> 12\text{cm}^2$ (large)
- Diabetic Foot Ulcer $\leq 2\text{cm}^2$ (small)
- Diabetic Foot Ulcer $> 2\text{cm}^2$ (large)

Further details regarding the randomization process will be provided in the SAP.

An interim analysis will be performed after 80 subjects have completed the study, incorporating a minimum of 40 VLU and 20 DFU.

CONFIDENTIAL DOCUMENT
This document contains confidential information, which is the property of Smith & Nephew, Inc. Do not copy, disclose, or circulate without written authorization from the appropriate Smith & Nephew personnel

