9.1.4 Study Visits 2-12

The treatment period is defined as Randomization Study Visit 1 through Study Visit 12. During the study treatment period, any AE associated with the target ulcer and all SAE of any kind will be recorded in the appropriate eCRF. Device deficiencies (DevD) will be recorded in a separate eCRF. The evaluation of all AE is described in Section 12, *Adverse Events*. All weekly visits

must be performed according to the study visit schedule (Section 17), preferably on the same day each week, to conduct all assessments and to assure compliance with treatment. A plus or minus one day visit window will be used for all study visits.

VLU subjects found to have target ulcer closure should continue the compression dressing. Appropriate treatment for DFU subjects found to have target ulcer closure is left to the Investigator's discretion. Appropriate treatment for VLU and DFU subjects, whose target ulcer is ready for and will be surgically closed, is left to the Investigator's discretion. If the Investigator believes the target ulcer is ready for surgical closure, then this procedure should be completed within the same week of the scheduled study visit. The next scheduled visit for subjects with closed target ulcers or subjects that will be surgically closed will be designated as End of Treatment Assessment Visit 14 and should occur in 7 (± 1) days.

All study procedures should occur in the order outlined in the protocol. Study Visits occurring outside the protocol specified visit window should be completed and recorded as a protocol deviation.

1. Subjects will be queried regarding any changes in general health and the use of concomitant medications.
2. Any AE associated with the target ulcer and all SAE of any kind reported since the last assessment will be recorded in the appropriate eCRF. DevD will be recorded in a separate eCRF (see "Section 12, *Adverse Events*" for reporting and evaluating AE). Also, subjects will be queried as to any additional ulcer-related interventions requiring hospital admission, surgical intervention or specialist referral since the last assessment.
3. Assess level of pain from NPWT dressing wear, since the previous study visit, using the VAS.
4. Prior to examination of the ulcer, remove compression bandaging (**for VLU subjects**) and photograph the NPWT topical dressing using the ARANZ Silhouette wound imaging and measurement device.

CONFIDENTIAL DOCUMENT

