2. STUDY DESIGN

2.1 DESCRIPTION OF TRIAL DESIGN

This is a multi-center, Phase 4, randomized, open-labelled, comparative-effectiveness study in subjects with at least one lower extremity wound (VLU or DFU). Subjects will be randomized to one of two treatment groups to receive either PICO single-use NPWT system or ActiV.A.C. ® System, for 12 weeks, or until target ulcer closure (by surgical intervention or secondary intention), whichever occurs first.

The study consists of four periods: a 1-week run-in period (including screening Run-In Visit 1, Run-In Visit 2), a 12-week randomized treatment period (including Study Visit 1 through Study Visit 12), a 1-week end-of-treatment assessment period (including Study Visits 13, 14). Study Visit 14 serves as the end of study visit.

Following a 1-week run-in period, approximately 160 subjects meeting entry criteria will be randomly assigned to one of the two treatment arms in a 1:1 allocation ratio to receive treatment with either PICO single-use NPWT system or ActiV.A.C. ® system for 12 weeks with dressing changes as deemed required in the opinion of the investigator or required in the instructions for use (IFU).

Eligible subjects will receive treatment for 12 weeks (Visits 1 through 12), or until their wound closes or progressing sufficiently to become ready for surgical closure in the opinion of the investigator. Subjects whose wounds have closed, as assessed by the Investigator, prior to the 12th week of treatment (or Visit 12) will stop treatment and return for one further visit (Visit 14) to verify if the target ulcer remains closed for one week following the initial observation of ulcer closure. An ulcer which remains closed at this one week verification assessment is defined as having achieved complete wound closure in this study.

For those subjects who are randomized and who discontinue from the study prior to Visit 13 due to any reasons other than target wound closure, Visit 14 will serve as the early termination (ET) visit.

The size of the target ulcer, pain associated with target ulcer will be assessed for each subject at Run-In Visit 1 (screening). This information, along with the status of

Document Number: 1004313
Document Version: 06

Document Part: 000
Document Status: Released

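### The interim set is the first 80 subjects to finish, and closed ulcers finish early; if the arms close at different speeds, the stop/go comparison leans toward the faster arm

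*SAP*

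**What the plan says.** The trigger is a count of completions in both documents. SAP 3.3: "An interim analysis of key variables will take place after approximately 50% of target recruitment (80 subjects completed". Protocol 8.1: "An interim analysis will be performed after 80 subjects have completed the study, incorporating a minimum of 40 VLU and 20 DFU". The Protocol synopsis, Protocol 7.1 and 11 and SAP 3.1 agree. The minimum numbers of VLU and DFU are the only rule on who is in the set.

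Time to completion depends on outcome. Protocol 9.1.4: "The next scheduled visit for subjects with closed target ulcers or subjects that will be surgically closed will be designated as End of Treatment", and that visit falls 7 (±1) days later. SAP 2.1 says that subjects whose wounds have closed "will stop treatment and return for one further visit (Visit 14) to verify if the target ulcer remains closed for one week". Protocol 9.1.6 then exits the subject. Closure can be recorded from Visit 2 (SAP 2.3.2). Subjects whose ulcers stay open finish at about week 12.

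Protocol 9.4 and SAP 2.3.1 set the area of a closed ulcer to 0, even before the one-week confirmation.

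Neither document defines what counts as completed, names the interim analysis population, or says what happens to subjects still on treatment at the look.

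**The concern.** Take the subjects randomized less than 12 weeks before the trigger. Those whose ulcers closed early can already be among the 80, each at 100% reduction. Those randomized at the same time whose ulcers are still open cannot. The set is therefore enriched for the best score.

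That enrichment matters for the comparison when it differs between arms, which happens when one arm closes sooner. Time to closure is itself a secondary objective, so the interim test should not rely on the arms being equal in it. Two arms with the same week-12 result but different closure timing would show a false difference at the one look that can lead to a recommendation to end the trial.

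**Working it through.** **Inputs from the documents.** SAP 3.1: "Using a non-inferiority margin of 12.5%, a sample size of 128 subjects". Its target is 80% power with a total one-sided alpha of 0.025. The planned mean is 60 and the SD 24.5, and 20% drop-out leads to 160 randomized 1:1. SAP 3.3: efficacy bound Z > 2.963, futility bound Z < 0.559.

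**The plan's own sample size.** A fixed design with margin 12.5 and SD 24.5 needs 61 per arm, or 122. A two-look calculation (information fraction 0.5, bounds 2.963 and 0.559, final critical value 1.969 solved for total one-sided alpha 0.025) gives 80.2% power at 128, and 128 / 0.80 = 160. The stated figures reproduce.

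**Interim look without selection.** With 40 completers per arm, SE = 24.5 × √(2/40) = 5.48. If the arms are truly equal, Z has mean 12.5 / 5.48 = 2.28.
- Efficacy crossing: 1 − Φ(2.963 − 2.28), about 25%.
- Futility crossing: Φ(0.559 − 2.28), about 4%.
- With PICO truly 12.5 points worse, efficacy crossing is 1 − Φ(2.963) = 0.0015, which rounds to the stated spend of 0.002.

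**How much closure the plan's mean and SD allow.** Let a share p close and score 100, with overall mean 60. The others average (60 − 100p)/(1 − p), so the variance between closed and open ulcers alone is 1600 × p/(1 − p). This cannot exceed 24.5² = 600.25. Hence p/(1 − p) ≤ 0.375 and p ≤ about 27%.

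**Simulation.** Drop-outs do not count as completers. Closed ulcers finish one week after closure and the rest at week 12. The first 80 to finish are compared with the first 80 non-drop-outs in order of randomization. Accrual (2-6 per week), closure share and closure weeks are assumptions; the documents give none of them.

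| Case | Result with the first 80 to finish |
|---|---|
| Same closure speed in both arms | Arm means rise; difference unbiased |
| Equal week-12 results, closure at weeks 2-7 versus 7-12, 15-25% closing | False difference about 0.5-3.0 points toward the faster arm |
| Equal week-12 results, weeks 4-9 versus 6-11, 20% closing | About 0.3-0.8 points |
| Equal, weeks 2-7 versus 7-12, 4 per week, 25% closing, PICO slower | Futility crossing about 4% → 8% |
| The same, PICO faster | Efficacy crossing about 25% → 35% |
| PICO truly 12.5 worse but closing faster, 20% closing | Efficacy crossing about 0.2% → 0.3-0.7% |

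Taking the set in order of randomization brings the false difference to about 0.0 in every case.

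**Cross-check by the normal formula.** A shift of 1.7 points, inside the 0.5-3.0 range, reproduces the fourth and fifth rows.
- Against PICO: Φ(0.559 − 10.8/5.48) = Φ(−1.41), about 8%.
- For PICO: 1 − Φ(2.963 − 14.2/5.48) = 1 − Φ(0.37), about 35%.

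**Limit of the last row.** If PICO is 12.5 worse, its mean is 47.5. The variance between closed and open ulcers is then 52.5² × p/(1 − p), so the cap at SD 24.5 falls to 600.25 / (600.25 + 2756.25) = 18%. Closure of 20% there needs an SD of at least 52.5 × √0.25 = 26.25, slightly above plan. At 10% closure, which fits the plan, with mean closure weeks of 4 and 9 and accrual of 2-8 per week, the rise is from 0.15% to 0.21-0.43%.

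**The case against.** **The effect is small and conditional.** This stands. With equal closure speed the difference is unbiased, with overlapping windows the shift is under 1 point, and with slow accrual it is near the bottom of the range. The documents give no closure speeds. Their comparative background (Protocol 4.2 and 4.3) describes similar area reduction between PICO and traditional NPWT, and non-inferiority of another single-use device. A reader might infer that the trigger favours one particular arm; nothing in the documents says which arm closes faster, if either.

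**A larger effect is tempting to infer.** Assuming 40% or 50% closure gives shifts that are a large part of the margin. The plan's figures do not support this: at mean 60, 40% closure needs an SD of at least √(1600 × 0.4/0.6) = 32.7, and 50% needs at least 40.

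**The reading of completed could differ.** Protocol 9.4 and SAP 2.3.1 speak of subjects withdrawn prematurely due to closure. If such subjects were not counted as completers, the set would still be selected on outcome, in the opposite direction. Early discontinuers, including those removed for a 75% area increase (Protocol 9.2), would add selection against the enrichment if counted. They would not reliably cancel it: the primary analysis is Per Protocol, which drops those who discontinue within nine weeks but keeps closures whatever their time on therapy (SAP 4.4 and 4.9). The interim population is not stated.

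**The consequence is soft.** The futility bound is non-binding, and crossing either bound yields only a recommendation. That limits the harm, but the recommendation should still rest on an unselected set.

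**Conclusion.** The point holds as a cheap improvement. Following the trigger as written selects the interim set partly on outcome and biases the arm difference toward the faster-closing arm when closure speeds differ. At the SAP's mean, SD and drop-out rate, the bias is about 0.5-3.0 points under strongly different closure timing, or roughly 0.1-0.5 of the interim SE (0.5/5.48 to 3.0/5.48). It does not reach the 12.5 margin in any case tried. Its main effect is on the chance of a stop recommendation when the arms are truly equal. The rise in false efficacy is small in absolute terms, and its upper figure of 0.7% assumes slightly more spread than the plan allows.

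The size rests on assumed accrual, closure share and closure timing, and on counting closures but not drop-outs as completed. The existence and direction of the selection, on that reading, rest on the text alone.

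**What to change.** In SAP 3.3, with matching text in SAP 3.1, the Protocol synopsis and Protocol 7.1, 8.1 and 11:

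- Define the interim cohort in order of randomization, extended in that order until it contains 80 subjects who complete, either by closure or by reaching week 12, including at least 40 VLU and 20 DFU.
- Run the look only when every cohort member has passed the week-12 visit date or discontinued.
- Exclude later-randomized subjects from the interim test, even if their ulcers have already closed.
- Handle discontinuers within the cohort by the same population rules as the final analysis.

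Fixing the cohort at the first 80 randomized would not do: at 20% drop-out it holds about 80 × 0.80 = 64 completers and cuts the interim information. Extending it to 80 completers avoids that. The cost is a few sentences and a look about 0.5-1 week later in the simulations.

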4. ANALYSIS PLAN

4.1 General

Smith & Nephew Wound Management Global Medical and Clinical Affairs will conduct data management and statistical analysis. Unless otherwise stated, all significance tests will be two-sided tests at the 5% significance level. P-values will be quoted and 95% confidence intervals will be generated where appropriate. All p-values will be rounded to three decimal places, p-values less than 0.001 will be presented as '<0.001' in all tables.

All descriptive statistics will be summarized by treatment (PICO or ActiV.A.C.®) and by target ulcer type (Venous Leg Ulcer or Diabetic Foot Ulcer) and combined ulcer types. All summaries will be repeated separately by site. In addition, all wound progress summaries [primary variable, proportion of patients (and time to) achieve

confirmed closure] for the ActiV.A.C.® treatment arm will be separated by predominant therapy used, either continuous or intermittent therapy, and overall.

Modifications to this summary approach, including additional variables of separation, will be defined where necessary in the following sections.

Subjects are able to be re-screened up to a maximum of two times in the case of screen failure. This results in a maximum of three screening periods (Run-In Visit 1:Run-In Visit 2) per subject. In the case of multiple screening periods being conducted, unless otherwise stated, the following summaries should include only the last screening period conducted for a given subject. Unless otherwise defined, baseline is defined as Study Visit 1.

4.2 Statistical Methods

Unless otherwise specified, all analyses will be performed in SAS v9.4 (or later).

Where data summaries are specified, categorical and ordinal variables will be summarized using frequency distributions which will detail the number and percentage of subjects which fall into each category. Continuous variables will be summarized using the following summary statistics: mean, median, standard deviation, minimum and maximum values, and number of observations.

4.3 Derived Data

1. A flag for patient inclusion in the full analysis set. If the patient has received NPWT and has at least one (post-baseline) dressing change assessment then the patient is included in the full analysis set. Otherwise the patient is excluded from the full analysis set.
2. A flag for patient inclusion in the safety population. If the patient has received NPWT, then the patient is included in the safety population. Otherwise the patient is excluded from the safety population.
3. The duration in days between the baseline assessment (Randomization Study Visit 1) and each scheduled Study Visit (2-12) (scheduled every 7 days) and Study Visit 13 or 14.

ST:

9 7 5

Reference:

CE/052/PIC

Customer Code:

0 5

4. The duration in days between the Screening Run-In Visit 1 and Screening Run-In Visit 2.
5. A flag for whether the Screening Run-In Visit 2 occurred 7 (± 1) days after Screening Run-In Visit 1.
6. The duration in days between the baseline assessment (Randomization Study Visit 1) and each scheduled Study Visit (2-12) (scheduled every 7 days) and Study Visit 13/14.
7. A flag for whether study visits occurred weekly after the Randomization Visit as per the protocol. A separate flag should be derived for each study visit.
E.g. Study Visit 2 should occur at 7 (± 1) days after the Randomization Study Visit 1. Study Visit 3 should occur at 14 (± 1) days etc.
8. The duration in days between the Study Visits i and j (where $i \geq 1$ and $j = i + 1$)
9. Patient age (years) defined as: The date of the baseline assessment – date of birth/365.25
10. Patient body mass index defined as: $\text{Weight (kg)} / (\text{Height (cm}/100))^2$
11. Reference wound duration at point of randomisation will be derived as follows:
Date of Target onset date - Date of Randomization Visit 1
12. The (post-screening) study duration (in days) will be derived as follows:
Date of Study Completion - Date of Randomization Visit 1
13. The Screening duration (in days) will be derived as follows (separately for screening, re-screen 1 and re-screen 2 where appropriate):
Date of Run-In Visit 2 - Date of Run-In Visit 1
14. The number of screening periods per subject will be derived as:
No re-screening periods used = 1
A single re-screening period used = 2
Two re-screening periods used = 3

Document Number: 1004313
Document Version: 06

Document Part: 000
Document Status: Released

15. The change in target ulcer area during the screening period will be derived as (change in depth and volume will be derived using the same method):

$$Area_{Run-In\ 2} - Area_{Run-In\ 1}$$

16. The percentage change in target ulcer area during the screening period will be derived as (percentage change in depth and volume will be derived using the same method):

$$\left(\frac{Area_{Run-In\ 2} - Area_{Run-In\ 1}}{Area_{Run-In\ 1}} \right) \times 100$$

17. Target ulcer area is defined as surface area as measured by the ARANZ Silhouette Device at each study visit by the Investigator. For each study visit, the change in target ulcer area will be derived as (change in depth and volume will be derived using the same method):

$$\text{Change in target ulcer area at Study Visit } n = Area_{SVn} - Area_{SV1}$$

18. For each study visit, the percentage change in target ulcer area will be derived as (percentage change in depth and volume will be derived using the same method):

$$\text{Percentage change in target ulcer area at Study Visit } n = \left(\frac{Area_{SVn} - Area_{SV1}}{Area_{SV1}} \right) \times 100$$

For purposes of the primary analysis, the percentage change in target ulcer area will be derived as using LOCF within the 12-week treatment period. The percentage change in depth and volume will be derived using the same method.

19. The time to achieve confirmed ulcer closure in days will be derived as follows:
- For those subjects that achieve confirmed closure (derived variable 20):
Date of Study Visit where closure is first recorded – Date of Randomization
 - For those subjects that achieve closure but do not achieve confirmation (derived variable 20):
Date of Study Visit where closure is first recorded – Date of Randomization
 - For those subjects that do not achieve closure during the 12-week treatment period or withdraw early, the time to achieve confirmed ulcer closure will be defined as either: Date of last study visit attended – Date of Randomization;
Or 84 days, whichever occurs earlier.

20. Whether confirmed ulcer closure was achieved will be derived as follows:

- Ulcer Closed/Ready for surgical closure=Yes at last attended Study Visit i, Ulcer Closed=Yes at Follow up assessment (Visit 14). Confirmed Closure = Yes
- Ulcer Closed/Ready for surgical closure =Yes at last attended Study Visit i, Ulcer Closed=No at Follow up assessment (Visit 14). Confirmed Closure = No
- Ulcer Closed/Ready for surgical closure =Yes at last attended Study Visit i, Ulcer Closed=missing at Follow up assessment (Visit 14). Confirmed Closure = missing
- Ulcer Closed/Ready for surgical closure =No at last attended Study Visit i. Confirmed Closure = No

In cases where the ulcer closure status is missing at a Study Visit, the Last Observation Carried Forward (LOCF) method will be used.

21. The derivation for whether confirmed ulcer closure was achieved will be repeated to form two further separate variables, with the exceptions below:

- i. In cases where subjects had missing data over the confirmatory target ulcer closure period (1 week follow-up) and it is unknown whether the closure is confirmed, these will be imputed as: Confirmed Closure=No. All remaining scenarios will be derived as described in the previous derived variable.
- ii. In cases where subjects withdraw from the study prior to the end of the 12-week treatment period (except in cases where the ulcer has closed), the following will be imputed: Confirmed Closure=Yes. All remaining scenarios will be derived as described in the previous derived variable.

22. The components of the CWIS will be derived as follows at baseline and end of treatment.

a) Physical symptoms and daily living

Each individual response will be coded by the following formulae:

Document Number:	1004313	Document Part:	000
Document Version:	06	Document Status:	Released

ST:

9

7

5

Reference:

CE/052/PIC

Customer Code:

0

5

Not at all/Not applicable – 5

Seldom/Slightly – 4

Sometimes/Moderately – 3

Frequently/Quite a bit – 2

Always/Very – 1

An overall score for this domain will then be calculated as the sum of the 24 individual values (12 individual values each for experience and stress related measures).

The overall score will then be transformed onto a scale of 0-100 using the following formula:

$$[(\text{Overall actual score (sum of 24 individual scores)} - \text{minimum possible score}) / \text{range of possible scores}] * 100$$

If all 24 questions are completed, the minimum value =24 and the range of scores = (120 - 24) = 96

b) Social Life

Each individual response will be coded by the following formulae:

Not at all/Not applicable – 5

Seldom/Slightly – 4

Sometimes/Moderately – 3

Frequently/Quite a bit – 2

Always/Very – 1

An overall score for this domain will then be calculated as the sum of the 14 individual values (7 individual values each for experience and stress related measures).

The overall score will then be transformed onto a scale of 0-100 using the following formula:

$$[(\text{Overall actual score (sum of 14 individual scores)} - \text{minimum possible score}) / \text{range of possible scores}] * 100$$

If all 14 questions are completed, the minimum value =14 and the range of scores = (70 - 14) = 56

c) Well-being

Each individual response will be coded by the following formulae:

Document Number: 1004313

Document Part: 000

Document Version: 06

Document Status: Released

Strictly disagree – 5

Disagree – 4

Not sure – 3

Agree – 2

Strongly agree – 1

NOTE: 'I am confident that the wound(s) I have will heal' will be coded in reverse (strictly disagree-1, disagree-2, not sure-3, agree-4, strongly agree-5).

An overall score will be calculated as the average of the 7 individual values for the wellbeing domain.

The overall score will then be transformed onto a scale of 0-100 using the following formula:

$$\left[\frac{\text{Overall actual score (sum of 7 individual scores)} - \text{minimum possible score}}{\text{range of possible score}} \right] * 100$$

If all 7 questions are completed, the minimum value =7 and the range of scores = (35 - 7) = 28

23. The change in each of the CWIS scores (Wellbeing, Physical symptoms and daily living, Social life, Overall HRQoL and Patient Satisfaction with overall HRQoL) between baseline and end of treatment period will be derived separately as:

$$\text{Score at Baseline (Randomization)} - \text{Score at End of Treatment}$$

24. The responses to the individual EQ-5D-5L domains will be coded as detailed in the references (§6) for the Mobility, Self-care, Usual Activities, Pain/Discomfort and Anxiety/Depression domains. The individual domain responses on a scale of 1-5 will be combined in the previously defined order to form a 5-digit number in the form XXXXX (where X is 1-5) describing the respondent's health state.

25. The change in EQ-5D VAS between baseline and end of treatment period will be derived as:

$$\text{Score at Baseline (Randomization)} - \text{Score at End of Treatment}$$

26. The duration of dressing wear (dressing level) for each individual dressing will be derived as follows per assessment:

Document Number:	1004313	Document Part:	000
Document Version:	06	Document Status:	Released

ST:

9 7 5

Reference:

CE/052/PIC

Customer Code:

0 5

If no unscheduled visit takes place between consecutive assessments:

Duration of wear = Date of removal visit – Date of application visit – duration of study therapy interruption

If an unscheduled visit takes place between consecutive assessments multiple duration of wear values will be derived:

Duration of wear 1= Date of unscheduled visit – Date of application study visit

Duration of wear 2= Date of removal study visit – Date of unscheduled visit – duration of study therapy interruption

If more than one unscheduled visit occurs between consecutive assessments, further multiple wear times will be derived as above.

27. The average wear time per patient (patient level) will be derived as follows per subject:

Sum of duration of dressing wear (dressing level) values / Count of duration of dressing wear (dressing level) values

28. The median value for the baseline (Run-In Visit 2/Study Visit 1) target ulcer area will be derived for both the Full Analysis Set and Per Protocol populations by wound type and overall. The median value will also be derived for the depth and volume.

29. Whether or not the reference ulcer is clinically infected at any Study Visit.

30. Whether or not the reference ulcer has signs of infection at any Study Visit.

31. Whether an intervention was required will be derived for each subject:

If an unscheduled visit is recorded, where the reason for intervention is not given as routine: Intervention = Yes

If no unscheduled visits are recorded: Intervention = No

32. Whether prescription of an antibiotic was required will be derived for each subject:

If "have any systemic antibiotics been prescribed" = Yes at any assessment, or any antibiotic medications are recorded on the concomitant medications form, with a start date after randomization: Antibiotic = Yes

Document Number: 1004313

Document Version: 06

Document Part: 000

Document Status: Released

If "have any systemic antibiotics been prescribed" = No at all assessments, and no antibiotic medications are recorded on the concomitant medications form:
Antibiotic = No

33. Whether an intervention or prescription of an antibiotic was required will be derived for each subject:
If Intervention derivation (Derived Variable 31) = Yes or Antibiotic derivation (Derived Variable 32) = Yes, then need for intervention or antibiotic= Yes
If Intervention derivation (Derived Variable 31) = No or Antibiotic derivation (Derived Variable 32) = No, then need for intervention or antibiotic= No
34. All pain assessments (dressing removal, during wear, on initiation of therapy) will be derived as follows:
In cases where pain = No, the VAS pain value will be coded as 0
35. Level of Exudate (amount) will be coded as follows- In cases where Exudate presence=No, then the level/amount of exudate will be coded as None.
36. The responses to the aspects of the wound assessment tool (BWAT-M); Undermining, Necrotic Tissue Type, Necrotic Tissue Type, Necrotic Tissue Amount, Exudate Type, Exudate Amount, Skin Color Surrounding Wound, Granulation Tissue and Epithelialization will be coded at each study visit as defined in Section 7. The individual coded values will then be summed at each individual study visit to give a total wound status score.
37. The personnel time taken at each Study Visit will be derived as:
No. of personnel applying the dressing x time taken to apply the NPWT system
38. The total personnel time taken at throughout the study will be the sum of the personnel time at Study Visits per subject.
39. The duration for which compression therapy was interrupted at each Study Visit in hours will be derived as: hours + (daysx24). If no interruption is recorded then the number of hours will be coded as 0.

ST:

9 7 5

Reference:

CE/052/PIC

Customer Code:

0 5

40. The duration for which study therapy was interrupted at each Study Visit in hours will be derived as: hours + (daysx24). If no interruption is recorded then the number of hours will be coded as 0.
41. The total duration (in hours) for which compression therapy was interrupted per subject will be calculated as the sum of the interrupted duration at each Study Visit.
42. The total duration (in hours) for which study therapy was interrupted per subject will be calculated as the sum of the interrupted duration at each Study Visit.
43. In cases where the ulcer is recorded as closed in the investigators opinion the following imputations will be made if missing values are present:
- Presence of infection = No
 - Presence of clinical signs of infection = No
 - Level of Exudate = None/No
 - Extent of undermining = None
 - Necrotic tissue present = No
 - Epithelialization at target ulcer = 100% wound covered, surface intact
44. Individual flags for whether each event was a serious adverse event, severe adverse event, investigational device related adverse event, a serious investigational device related adverse event, an unexpected adverse event and a serious unexpected adverse event.
45. Individual flags for whether a patient experiences: a serious adverse event, severe adverse event, investigational device related adverse event, a serious investigational device related adverse event, an unexpected adverse event and a serious unexpected adverse event.
46. The duration of resolved adverse event in days defined as: End date – start date.
47. The duration of adverse events at study completion defined as:
End date – start date for adverse events that resolved during the study period.
Date of study completion – start date for adverse events with no end date.

Document Number: 1004313
Document Version: 06

Document Part: 000
Document Status: Released

